Patients completing or withdrawing from the study will be followed up for survival information until database lock. Any patients who discontinue study treatment for reasons other than progression, and for whom no further treatment is deemed appropriate or desired, should remain on study and have scheduled scans until documented progression.

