#### 11.3 LEVEL OF SIGNIFICANCE

In this non-comparative study, all endpoints will be presented descriptively only, with no formal statistical analysis performed. Hence no formal statistical hypothesis testing will be carried out. The interpretation of p-values will be in the descriptive sense only and no levels of significance will be applied.

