3 SAMPLE SIZE

Sufficient patients will be screened for 18 patients to be enrolled into cohort A and 8 into cohort B of this open-label study. Patients withdrawn during the course of the

study will not be replaced. No formal sample size calculation has been performed and the sample size is considered a sufficient and adequate number of patients to investigate the efficacy signals of IMM-101 combined with nivolumab in controlling advanced melanoma and to explore the safety profile of the combination therapy.

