5.13.2 Secondary Endpoints

5.13.2.1 PFS Assessed by RECIST 1.1 for Cohorts A and B

PFS will be analysed using the ITT set and analysis will be repeated for the PPS for Cohort A only.

PFS is defined in months as the time between Visit 1 and the first confirmation of progression using RECIST 1.1, or death from any cause (whichever occurs first) (date

of first progression or death – date of Visit 1 + 1). Progression is determined by the investigator using the CT or MRI scan (scheduled or unscheduled) or death due to any cause. Subjects who die without reported progression will be considered to have progressed on the date of their death.

The following censoring rules will apply:

- Subjects who did not progress or die will be right censored on the date of their last evaluable tumour assessment.
- Subjects who did not have any on-study tumour assessments (scans) and did not die will be right censored on their date of first post-Screening visit. Note that this definition is consistent with that used for [Checkmate 067](#)².
- Subjects who remain on study following radiotherapy or other prohibited treatment will be censored at their last scan assessment prior to the intervention therapy.
- Subjects in Cohort B who change therapy to IMM-101 + ipilimumab without documented progression by RECIST 1.1 will be censored at the date of their last evaluable tumour assessment prior to this change in therapy.

Summaries of PFS

Descriptive statistics will be presented for PFS. The number and percentage of subjects that are censored will be summarised, along with KM estimates for the 25th, 50th and 75th percentiles of PFS and corresponding 95% CIs. PFS will also be presented graphically using a KM plot. The proportion of subjects who have not progressed or died at three monthly intervals will also be presented.

A time to event listing will present the milestones required for calculation of each time to event efficacy parameter.

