5.13.2.2 OS and OS at 1 Year for Cohorts A and B

OS and OS at one year will be analysed using the ITT set and analysis will be repeated for the PPS for Cohort A only.

OS is defined in months as the time between Visit 1 and the date of death from any cause (date of death – date of Visit 1 + 1).

OS will be calculated for the entire study duration where subjects without a death date will be right censored at the date the subject was last known to be alive (during or post study). Post-study survival information is collected until database lock, for subjects completing or withdrawing from the study.

OS will also be calculated for subjects at one year, where subjects without a death date will be right censored on the date of Visit 1 + 365 days.

Summaries of OS

Descriptive statistics will be presented for OS for the whole study period and repeated for OS at one year. The number and percentage of subjects that are censored will be summarised, along with KM estimates for the 25th, 50th and 75th percentiles for both OS and OS at one year and corresponding 95% CIs for each. OS and OS at one year will also be presented graphically using a KM plot. The proportion of subjects alive at 3 monthly intervals will also be presented.

Survival status and death details (during or post study) will be listed for each subject.

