5.13.3.2 Duration of Response Assessed by RECIST 1.1 for Cohorts A and B

Duration of response will be analysed using the ITT set and only subjects who have a documented response of CR or PR will be included.

Duration of response is calculated as the time in months from the date of first documented response of CR or PR per RECIST 1.1 until the date of documented PD per RECIST 1.1 or until the date of death due to any cause (date of death or PD – date of documented response + 1). All scans are considered, whether scheduled or unscheduled, in the determination of response and confirmed responses are not required.

Subjects who neither progress nor die will be right censored on the date of their last tumour assessment. For Cohort B subjects who change treatment to IMM-101 and ipilimumab, only responses evaluated until the point of this change in therapy are included.

Summaries of duration of response

Descriptive statistics will be presented for duration of response. The number and percentage of subjects that are censored will be summarised, along with KM estimates for the 25th, 50th and 75th percentiles for the duration of response and corresponding

95% CIs. The proportion of subjects who have not progressed or died following a complete or partial response at three monthly intervals will also be presented.

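### PFS and duration of response count deaths without a time limit after imaging has ended, so the Kaplan-Meier tail, and any percentile falling after Week 80, is an artefact

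*SAP*

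**What the plan says.** For PFS, SAP 5.13.2.1 has two rules that work on different clocks. On deaths: "Subjects who die without reported progression will be considered to have progressed on the date of their death". On survivors: "Subjects who did not progress or die will be right censored on the date of their last evaluable tumour assessment". Protocol 5.2.2 and 10.2 carry the same pair.

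For duration of response, SAP 5.13.3.2 (and protocol 10.1.3) also ends the interval at progression or any death, and on the rest says: "Subjects who neither progress nor die will be right censored on the date of their last tumour assessment".

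Vital status is followed well beyond imaging. The protocol's Treatment Phase text in section 5.1 says: "Patients completing or withdrawing from the study will be followed up for survival information until database lock". SAP 5.13.2.2, on OS, says: "Post-study survival information is collected until database lock, for subjects completing or withdrawing from the study".

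Imaging stops earlier. Protocol 8.2 and Appendix 1 place the last scheduled scan at Week 76 (A) or Week 78 (B). Protocol 8.3 adds a scan at the End of Study visit (Week 80) only if the previous one is more than 8 weeks old (12 weeks if that scan was after Week 52) and progression is not already documented.

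For PFS the SAP will print the three quartiles with 95% CIs, three-monthly proportions and a Kaplan-Meier plot; for duration of response, the quartiles and proportions. Neither document closes these endpoints at the end of imaging. The sensitivity analyses in SAP 5.13.1 concern best overall response only.

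**The concern.** Kaplan-Meier estimation needs censoring that does not depend on what happens later. Here it does. A patient who finishes the study progression-free and survives leaves the risk set at the Week 76 or 78 scan. An identical patient who later dies stays at risk until the death. Once the last scans are past, the only people left at risk are those with a death on file.

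PFS is the first-listed secondary efficacy endpoint, and SAP 2.1 says efficacy will be compared with published data on nivolumab alone. A finite median, or a curve that drops to zero, could be set beside published curves although it was produced by one or two deaths with no imaging in between.

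**Working it through.** **Inputs from the documents.** Cohort sizes of 18 and 8 (SAP 3). Event and censoring rules as above. First scan at Week 12 (A) or Week 6 (B), last scheduled scan at Week 76 or 78. The End of Study visit is 28 ± 7 days after the last IMM-101 dose, which is scheduled at Week 76, so it falls by about Week 81. The plan states no PFS figure to reproduce: "No formal sample size calculation has been performed".

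**Conversion** (weeks × 7 / 30.4375). Week 76 = 17.5 months, Week 78 = 17.9, Week 80 = 18.4.

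**Risk set after imaging.** The estimate is S(t) = Π(1 − dᵢ/nᵢ). After about Week 81 every event-free survivor has been censored, so nᵢ counts only patients with a later death. At the last of these deaths n = d, the factor is 0, and S = 0 whatever its value before.

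**Worked cases, n = 18.**
- 8 progressions, 9 censored at Week 76, one death at month 30. At Week 76, S = 10/18 = 0.556. One patient remains, so S = 0.556 × (1 − 1/1) = 0. The median changes from not reached to 30 months.
- 10 events, 7 censored at Week 76, one death at month 30. S = 8/18 = 0.444, then 0. The 75th percentile becomes 30 months.
- 8 progressions, 8 censored at Week 76, deaths at months 20 and 24. S = 0.556 × (1 − 1/2) = 0.278, then 0. The median becomes 20 months.

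**Duration of response.** The latest scheduled-scan censoring time is 76 − 12 = 64 weeks (14.7 months) in A and 78 − 6 = 72 weeks (16.6 months) in B. Beyond that only deaths remain.

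**How often.** A simulation (1,500 runs per scenario) used the protocol scan weeks and the SAP rules. Assumptions not in the documents: median time to progression 6, 12 or 24 months; median survival after progression 12 months; death without progression 0.005 per month; withdrawal 0.01 per month; accrual over 6 or 24 months; lock 2 or 6 months after the last patient's Week 80. The table gives the percentage of trials whose PFS curve falls to zero after Week 80. In every scenario this equals the percentage with at least one death after Week 80 without documented progression.

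| Cohort, median time to progression | Accrual 6, lock +2 | Accrual 24, lock +2 | Accrual 24, lock +6 |
|---|---|---|---|
| A, 6 months | 28.7 | 63.2 | 73.9 |
| A, 12 months | 42.3 | 85.0 | 91.2 |
| A, 24 months | 43.7 | 85.5 | 93.4 |
| B, 6 months | 12.5 | 32.9 | 41.2 |
| B, 12 months | 20.1 | 49.0 | 57.8 |
| B, 24 months | 18.7 | 50.1 | 65.7 |

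The comparator counted only deaths within 16 weeks of the last scan. With a 24-month median, a median not reached under the comparator became finite under the SAP rule in 19.9–47.2% of runs (A) and 9.3–34.7% (B). In cohort A with 24-month accrual, mean estimated PFS at 36 months was 0.11–0.12 against a true 0.29. At 18 months the largest shift between the two rules was 0.135 − 0.118 = 0.017.

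**The case against.** **Death is a standard PFS event, and the plan is descriptive.** Both are true. Protocol 11.3 says: "The interpretation of p-values will be in the descriptive sense only and no levels of significance will be applied". PFS is secondary, duration of response is exploratory, and the PFS objective concerns at most 18 months of treatment, a period in which the rule does little harm. This limits the severity. It does not rescue the tail: when everything is descriptive, the printed quartiles and curve are the result.

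**Some patients keep being scanned.** Protocol 5.1, 5.3, 6.3 and 6.4 keep patients who stop treatment without progression, and need no other therapy, on scheduled scans until progression. But Appendix 1 schedules none after the End of Study visit, and patients who complete the study have none.

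**The SAP cites CheckMate 067.** That remark is attached to the rule for patients with no scans, not to late deaths.

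**Stronger readings.** A reader might infer that every death up to database lock is a PFS event. The documents do not say so. Deaths after documented progression do not count; nor do those after on-study prohibited therapy, or after a cohort B switch to ipilimumab without progression. The SAP gives no closing date for PFS. Only the OS section refers explicitly to deaths after the study, and protocol 5.2.2 assesses secondary endpoints at the end of the study, defined in 18.7.1 as the last patient's last visit. Lock is therefore an inference. The problem survives either reading: protocol version 1.0 dates from April 2018 and recruitment was suspended in March 2020, so early enrollees could be followed for many months after their own last scan.

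A reader might also infer that the whole PFS analysis is invalid. It is not. Early leavers who later die are kept at risk in the same way before Week 80, but in the simulation the effect at 18 months stayed below 0.02.

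**Conclusion.** The concern holds for the tail, and it should be fixed. That the curve falls to zero at the last post-imaging death follows from the rules and needs no assumption. Any PFS median or 75th percentile after Week 80, and the corresponding late part of the duration-of-response curve, is an artefact. PFS up to 18 months is little affected and ORR is unaffected.

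How often it happens does rest on assumptions: roughly 30–90% of cohort A trials and 13–66% of cohort B trials over the scenarios shown. The documents give no lock date, and timing matters. In a separate simulation (n = 18, 20% leaving early, median survival after progression 15 months, true median PFS 8 or 14 months), moving the assumed lock from 24–42 to 19–30 months after entry cut the rate of late deaths from about 77–81% to about 39–42%.

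**What to change.** In SAP 5.13.2.1 and 5.13.3.2, set a cut-off at the end of scheduled imaging, taken as each patient's Week 80.
- Count progression or death up to the cut-off as an event. Otherwise censor at the last evaluable scan.
- End the PFS curve, percentiles and three-monthly proportions there. For duration of response, use the matching time from first response, at most 80 − 12 = 68 weeks (A) or 80 − 6 = 74 weeks (B).
- Report later deaths in OS only, and keep the all-deaths version as a sensitivity analysis.
- A limit on missed scan intervals can be a further sensitivity analysis.

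Do not also require the death to precede the End of Study visit. That would censor patients who leave while deteriorating and die soon after, which favours the treatment; in simulation it raised PFS at about 17.4 months by roughly 0.02–0.04 over the SAP rule. The visit also takes place only where possible, so the condition would sometimes be undefined.

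A small residue remains. A death between the last scheduled scan and Week 80 (4 weeks in A, 2 in B) still meets a depleted risk set. At the assumed 0.005 per month, ten progression-free patients over 28/30.4375 = 0.92 months give 10 × 0.005 × 0.92 = 0.046 expected deaths, not counting deaths after undetected progression. Numbers at risk under the plot would make this visible.

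The death rule is also in the protocol, so the change should be recorded and justified in SAP section 6, as protocol 11.6 requires. The cost is SAP wording and programming, with no new data. The downside is slightly fewer events, and some upper percentiles that will read as not reached.

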# 7.6.2 **Ipilimumab**

If used on study for patients in cohort B, ipilimumab is to be administered as a 3 mg/kg IV infusion over 90 minutes every three weeks for a maximum of 4 doses, in accordance with the prescribing information. The first dose of ipilimumab can start at any time during the study but must be at least 2 weeks after the last dose of nivolumab. In instances when ipilimumab and IMM-101 are given on the same day, IMM-101 will be administered first.

In the event of toxicity, doses may be delayed (see section 7.2.1), but all ipilimumab doses must be administered within 16 weeks of the first dose.

Patients in cohort B who receive all 4 doses of ipilimumab should remain on study after this time and follow the protocol assessments. They may continue to receive IMM-101 during this period until unacceptable side-effects, the Investigator's decision to discontinue treatment, withdrawal of patient consent or 18 months of IMM-101 treatment, whichever is the sooner.

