#### 8.5.1 Tumour Burden

During the study, response will be assessed by CT or MRI, the same imaging method used at baseline (Screening) and during the remainder of the study for each patient. The preferred method is contrast enhanced CT of the chest, abdomen and pelvis. A baseline MRI of the brain should be done for patients with a history or clinical symptoms of brain metastases. MRI can be used as an alternative method to CT scan if the patient has a clinical contraindication for iodine-based IV contrast or to better assess the disease. CT head scan can be used as an alternative to MRI of the brain if IV gadolinium is contraindicated.

All baseline evaluations must be performed no more than 21 days before enrolment and should be as close as possible to the beginning of treatment. All known and suspected sites of disease should be assessed and at least one measurable lesion according to RECIST 1.1 criteria must be present at screening. A maximum of 5 target lesions can be recorded with a maximum of 2 lesions per organ representative of all involved organs (see Section 8.5.2.1). All measurements should be recorded in millimetres (mm). Imaging based evaluation should **always** be used

Page 58 of 98

rather than clinical examination unless the lesion(s) being followed cannot be imaged but are assessable by clinical exam.

All scans will be reviewed by experienced radiographers trained in the study requirements. The scans will be read in sequence, and each review should be within 4 weeks of the scan being conducted to ensure that a confirmatory scan can be conducted as required.

Baseline scans will be assessed (and non-target/target lesions identified from the baseline scan alone) prior to the review of post baseline scans.

Where possible, the same radiographer should review the scan for both RECIST 1.1 and irRC at the same time, and review all scans for the same patient.

Further details are provided in the IMM-101-015 Study Operations Manual.

Chest CT is preferred over chest x-ray, however lesions on chest x-ray may be considered measurable if they are clearly defined and surrounded by aerated lung.

Clinical lesions will only be considered measurable when they are superficial and  $\geq 10$  mm diameter by caliper measurement. For the case of skin lesions, documentation by colour photography using a ruler to estimate the size of the lesion is possible, but CT is always preferred.

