#### 8.5.2.3 Baseline Documentation of Lesions - irRC

Baseline scans will be assessed prior to availability of post baseline scans. Where possible, the same radiographer should review the scan for both RECIST and irRC at the same time, and review all scans for the same patient.

For irRC, up to five lesions in a single organ may be recorded with a maximum of 10 visceral and five cutaneous index lesions. At the baseline tumour assessment, the two largest perpendicular diameters of each target lesion are recorded and the sum of the products of the two largest perpendicular diameters of all index (target) lesions is calculated (SPD). At each subsequent tumour assessment, the SPD of the index lesions and of new, measurable lesions ( $\geq 5 \times 5$  mm) are added together to provide the total tumour burden:

Tumour Burden = SPDindex lesions + SPDnew, measurable lesions

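### Duration of response is censored at the last scan whether or not it is evaluable, while PFS generally requires an evaluable one; three PFS rules also lack a Visit 1 fallback

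*SAP*

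**What the plan says.** SAP 5.13.2.1 measures PFS as the date "of first progression or death – date of Visit 1 + 1" and gives four censoring rules, numbered here in the SAP's order:

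1. No progression or death: "Subjects who did not progress or die will be right censored on the date of their last evaluable tumour assessment".
2. No on-study scan at all and no death: censored at the first post-Screening visit, i.e. Visit 1.
3. Still on study after radiotherapy or another prohibited treatment: such subjects "will be censored at their last scan assessment prior to the intervention therapy".
4. Cohort B change to ipilimumab without RECIST 1.1 progression: such subjects "will be censored at the date of their last evaluable tumour assessment prior to this change in therapy".

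Protocol 5.2.2 and 10.2 carry rules 1, 2 and 4 in the same terms. Rule 3 appears only in the SAP.

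For duration of response, SAP 5.13.3.2 says: "Subjects who neither progress nor die will be right censored on the date of their last tumour assessment". Protocol 10.1.3 does the same.

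Protocol 8.5.3.9 makes a scan NE when only some of the lesions were measured, unless the missing ones could not have changed the result. On the timing of the baseline scan, Protocol 8.5.1 says: "All baseline evaluations must be performed no more than 21 days before enrolment".

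**The concern.** Two things are at issue.

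The first is a difference of one word. PFS rules 1 and 4 stop follow-up at the last scan that established disease status. Duration of response, and PFS rule 3, stop it at the last scan whether or not it established anything. The same patient can then be censored for PFS on one date and still be credited with an ongoing response on a later one. The error has one direction: it lengthens duration of response.

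The second is a missing fallback. Only rule 2 is anchored at Visit 1, and it covers only subjects with no on-study scan. A subject who has on-study scans, but no evaluable one before the censoring point, falls under rule 1, 3 or 4, and none of these says what date to use. The only earlier scan is the baseline scan, which normally precedes Visit 1. With cohorts of 18 and 8, the choice would be left to programming after the data are known.

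**Working it through.** The plan states no figure to reproduce, so the check applies its own date arithmetic. Days are counted from Visit 1 = day 0. Months use 30.4375 days, the divisor in SAP 5.7.3 and 5.12. The PFS and duration sections state months without a divisor, so this is an assumption.

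**Duration of response, worked example (assumed Cohort A patient).** Partial response at Week 12 (day 84) and again at Week 20 (day 140); NE scan at Week 28 (day 196); then no further scans, progression or death.

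- PFS, censored at the last evaluable scan: 140 − 0 + 1 = 141 days.
- Time to response: 84 − 0 + 1 = 85 days.
- Duration as written: 196 − 84 + 1 = 113 days. Then 85 + 113 − 1 = 197, which is 56 days beyond PFS.
- Duration to the last evaluable scan: 140 − 84 + 1 = 57 days. Then 85 + 57 − 1 = 141, which agrees with PFS.

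**General size.** The excess equals the gap between the last evaluable scan and the final NE scan.

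| Gap | Where it arises | Excess in months | With ±7 days on each scan |
|---|---|---|---|
| 28 days | confirmatory scan | 28 / 30.4375 = 0.92 | – |
| 56 days | routine 8-week interval | 56 / 30.4375 = 1.84 | 42 to 70 days: 1.38 to 2.30 |
| 84 days | optional after Week 52; also Week 16 to 28 after a confirmatory scan (Protocol 8.5.1) | 84 / 30.4375 = 2.76 | 70 to 98 days: 2.30 to 3.22 |

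**Effect on the Kaplan-Meier estimate (assumed data).** Take 8 responders, close to 44% of 18 = 7.92, using the nivolumab response rate cited in Protocol 3.4. Seven have events at 113, 169 and 225 days and censorings at 281, 337, 393 and 449. The eighth is the patient above.

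- Censored at 57: 6/7 = 0.857; × 5/6 = 0.714; × 4/5 = 0.571.
- Censored at 113, ties counted as at risk: 7/8 = 0.875; × 5/6 = 0.729; × 4/5 = 0.583.

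Later censoring can only enlarge the risk sets, so the estimate rises or stays the same.

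**PFS rule 3.** It names a scan without requiring it to be evaluable. An NE scan before the intervention therefore extends PFS by the same gap.

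**PFS with no evaluable on-study scan before the censoring point.** Three routes lead there:

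- Rule 1: every on-study scan is NE. SAP 5.13.1 foresees this and sets best overall response to progression, but there is no PFS counterpart.
- Rule 3: a prohibited treatment is given before the first scan.
- Rule 4: a Cohort B patient changes on clinical progression before the Week 6 scan or after an NE one. Protocol 7.6.2 says "The first dose of ipilimumab can start at any time during the study", subject to a 2-week gap from nivolumab.

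The SAP states no precedence when rule 2 and rule 3 or 4 both apply. If the baseline scan is used:

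- Scan 21 days before Visit 1: −21 + 1 = −20 days (−0.66 months).
- Scan 1 day before: −1 + 1 = 0 days.
- Same-day scan: 0 + 1 = 1 day, the value rule 2 gives.

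**Effect of that.** One such patient is 1/18 = 5.6% of Cohort A or 1/8 = 12.5% of Cohort B. Compared with Visit 1, the mean moves by at most 21 / 18 / 30.4375 = 0.04 months (A) or 21 / 8 / 30.4375 = 0.09 months (B), and the minimum can be negative. In an assumed set of 18, the Kaplan-Meier estimates were identical (0.8235, 0.6968, 0.5701, 0.4989 at successive event times) with that subject censored at −20, 0 or 1 day, or left out. A subject censored before the first event is in no risk set.

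**The case against.** The strongest reply concerns the baseline scan. Protocol 5.3 assigns response categories, including inevaluable, only to post-baseline scans, so a baseline scan is not naturally an evaluable tumour assessment. The phrase in "At the baseline tumour assessment, the two largest perpendicular diameters of each target lesion are recorded" comes from the irRC section (Protocol 8.5.2.3), whereas PFS is by RECIST 1.1. Rule 2 also suggests the authors meant Visit 1 as the floor. Most of this stands. A reader might infer that the plan instructs negative PFS times; the documents do not go that far. What they lack is a stated date. The text does not close the gap either: only rule 2 says on-study, Protocol 8.5.3.1 counts the baseline sum among those on study, and SAP 5.13.1 says post-baseline where it means that. Rule 3 is looser still, since it refers to any scan.

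The routes are also narrow. Protocol 8.5.1 allows earlier imaging when clinically indicated. Protocol 6.5.1 bars radiotherapy before the first scheduled assessment unless the Sponsor agrees, which leaves other prohibited treatment as the likelier route to rule 3. SAP 5.6 may remove some of these patients from the Cohort A per-protocol analysis. The planned time-to-event listing would show the dates.

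For duration of response, it could be argued that an NE scan is not an assessment. Protocol 8.5.3.9 speaks of an assessment that is NE, and PFS rules 1 and 4 add the qualifier explicitly, so its absence carries meaning.

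Two further inferences should be resisted. One is that survival software would discard negative times, so that the number analysed falls short of the ITT set; the documents do not say how such times would be handled. The other is that one patient would be 20% of Cohort B. The five subjects are the interim ORR set, and SAP Section 4 presents no other efficacy endpoint at the interim.

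**Conclusion.** The duration-of-response point holds. The rule differs from the main PFS rule by the missing requirement that the scan be evaluable. It overstates response by the last scan gap, about 1.8 months at 8 weeks and 2.8 months at 12, for any responder whose final scan was done but NE. PFS rule 3 shares the omission.

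The missing Visit 1 fallback in PFS rules 1, 3 and 4 is real but lesser. It could put a value of 0 to −20 days into the descriptive statistics and listing. It leaves the Kaplan-Meier curve unchanged unless an event falls by day 1.

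How many patients would be affected cannot be known from the documents; it may be none. Duration of response is exploratory, PFS is secondary, the study is descriptive, and the primary ORR does not depend on any of these rules. Priority: low.

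**What to change.** - SAP 5.13.3.2: censor at the last *evaluable* tumour assessment.
- SAP 5.13.2.1, rules 1, 3 and 4: censor at the last evaluable post-baseline tumour assessment before the censoring point, or at Visit 1 if there is none. This gives 1 day in the fallback case, as rule 2 does, and settles which rule prevails.
- SAP Section 6: record both as changes from Protocol 5.2.2, 10.1.3 and 10.2. Protocol 11.6 allows deviations from the planned analysis to be documented and justified in the final SAP. The same entry can note that rule 3 has no counterpart in the protocol.

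The cost is a few words in two SAP sections and one entry in Section 6. Duration of response, and PFS under rule 3, become slightly shorter for patients whose last relevant scan is NE. No data collection changes.
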